The ECGs will be evaluated by an appropriately trained physician at the site ("local reader"). The local reader from the site will sign, and date ECG tracings and will provide his/her global interpretation as a written comment on the tracing using the following categories:

Normal ECG

Abnormal ECG – not clinically significant

Abnormal ECG – clinically significant

Only the local reader's evaluation of the ECG will be collected and documented in the subject's source. The automatic machine reading (i.e., machine-generated measurements and interpretation that are automatically printed on the ECG tracing) will not be collected.

Clinical Laboratory Tests

Samples will be obtained at a minimum for the clinical laboratory tests outlined in [Table 8](#) at the visits indicated in [Table 7](#).

Blood samples for serum chemistry tests should ideally be collected following a minimum 8-hour fast at the following visits: Day 1, Final Treatment Visit, and PT Week 52, 104, 156, 208, and 260. The remaining visits may be non-fasting.

Subjects whose visits occur prior to the morning dose of study drug should be instructed to fast after midnight. Subjects whose visits occur following the morning dose of study drug should be instructed to fast after breakfast until the study visit occurs.

At the Day 1 study visit, a fasting blood sample is to be collected prior to the first dose of study drug which is administered at the Day 1 study visit. Blood samples should still be drawn if the subject did not fast for at least 8 hours. Subjects should be reminded to eat prior to their first dose of study drug (e.g., suggest they bring a light snack). Fasting status will be recorded in the source documents and on the laboratory requisition. The baseline laboratory test results for clinical assessment for a particular test will be defined as the last measurement prior to the initial dose of study drug.

A certified central laboratory will be utilized to process and provide results for the clinical laboratory tests. Instructions regarding the collection, processing, and shipping of these samples will be provided by the central laboratory chosen for this study. The certified laboratory chosen for this study is ICON. Samples will be sent to the following address:

ICON Central Laboratories
[name]
[name]

Table 8. Clinical Laboratory Tests

Hematology	Clinical Chemistry	Additional Tests
Hematocrit	Blood Urea Nitrogen (BUN)	HBsAg ^b

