CREATININE	1.5 – 1.7 mg/dL	1.8 – 2.0 mg/dL	2.1 – 2.5 mg/dL	>2.5 mg/dL or requires dialysis
GLUCOSE, SERUM, LOW	<LLN – 55 mg/dL <LLN – 3.0 mmol/L	<55 – 40 mg/dL <3.0 – 2.2 mmol/L	<40 – 30 mg/dL <2.2 – 1.7 mmol/L	<30 mg/dL <1.7 mmol/L
GLUCOSE, SERUM, HIGH (Fasting)	>ULN – 160 mg/dL >ULN – 8.9 mmol/L	>160 – 250 mg/dL >8.9 – 13.9 mmol/L	>250 – 500 mg/dL >13.9 – 27.8 mmol/L	>500 mg/dL >27.8 mmol/L or acidosis
MAGNESIUM, SERUM, LOW	<LLN – 1.2 mg/dL <LLN – 0.5 mmol/L	<1.2 – 0.9 mg/dL <0.5 – 0.4 mmol/L	<0.9 – 0.7 mg/dL <0.4 – 0.3 mmol/L	<0.7 mg/dL <0.3 mmol/L
MAGNESIUM, SERUM, HIGH	>ULN – 3.0 mg/dL >ULN – 1.23 mmol/L		>3.0 – 8.0 mg/dL >1.23 – 3.30 mmol/L	>8.0 mg/dL >3.30 mmol/L
PHOSPHATE, SERUM, LOW	<LLN – 2.5 mg/dL <LLN – 0.8 mmol/L	<2.5 – 2.0 mg/dL <0.8 – 0.6 mmol/L	<2.0 – 1.0 mg/dL <0.8 – 0.3 mmol/L	<1.0 mg/dL <0.3 mmol/L
POTASSIUM, SERUM, LOW	<LLN – 3.0 mmol/L		<3.0 – 2.5 mmol/L	<2.5 mmol/L
POTASSIUM, SERUM, HIGH	>ULN – 5.5 mmol/L	>5.5 – 6.0 mmol/L	>6.0 – 7.0 mmol/L	>7.0 mmol/L
PROTEIN, SERUM, LOW	5.5 – 6.0 g/dL	<5.5 – 5.0 g/dL	<5.0 g/dL	
SODIUM, SERUM, LOW	<LLN – 130 mmol/L		<130 – 120 mmol/L	<120 mmol/L
SODIUM, SERUM, HIGH	>ULN – 150 mmol/L	>150 – 155 mmol/L	>155 – 160 mmol/L Hospitalization may be indicated	>160 mmol/L
TRIGLYCERIDES HIGH (fasting)	150-300 mg/dL; 1.71 – 3.42 mmol/L	>300-600 mg/dL; >3.42-5.7 mmol/L	>500-1000 mg/dL; >5.7 – 11.4 mmol/L	>1000 mg/dL; >11.4 mmol/L
URIC ACID, SERUM, HIGH	7.5 – 10.0 mg/dL	10.1-12.0 mg/dL	12.1-15.0 mg/dL	>15.0 mg/dL

Clinical Toxicity Grades for HCV Studies
v1.1; 06 June 2009

Clinical Toxicity Grades for HCV Studies (Continued)				
	GRADE 1 TOXICITY	GRADE 2 TOXICITY	GRADE 3 TOXICITY	GRADE 4 TOXICITY
ENZYMES				
ALT/SGPT	>ULN - 3.0 × ULN	>3.0 - 5.0 × ULN;	>5.0 - 20.0 × ULN	>20.0 × ULN
AST/SGOT	>ULN - 3.0 × ULN	>3.0 - 5.0 × ULN;	>5.0 - 20.0 × ULN	>20.0 × ULN
ALKALINE PHOSPHATASE	>ULN - 2.5 × ULN	>2.5 - 5.0 × ULN	>5.0 - 20.0 × ULN	>20.0 × ULN
AMYLASE	>ULN - 1.5 × ULN	>1.5 - 2.0 × ULN	>2.0 - 5.0 × ULN	>5.0 × ULN
LIPASE	>ULN - 1.5 × ULN	>1.5 - 2.0 × ULN	>2.0 - 5.0 × ULN	>5.0 × ULN

- 1 Adapted from the National Cancer Institute's Common Terminology Criteria for Adverse Events v4.0 (CTCAE)
- 2 Used for all HCV development compounds

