Scheduled Time	Nominal Day (Study Day)	Time Window (Study Days Range)
Day 1/Baseline ^a	1	≤ 1
Week 2	14	2 to 21
Week 4	28	22 to 56
Week 12	84	57 to 126
Week 24 ^b	168	127 to 182
Final Treatment Visit ^c		2 to ≤ 2 days after last dose of study drug

a. Day of first dose of study drug.

b. Applicable to subjects with 24 weeks of treatment.

c. The last value within the window will be used to define the final on-treatment value. The upper bound of this Final window is Study Drug End Day ≤ 2.

Note: The result closest to the scheduled time point will be used. Data must also be ≤ 2 days of the last dose of study drug. Total Insulin is measured at baseline, Week 12, Week 24 (for subjects on 24-week treatment regimen only), or EOT, and will use those visit windows as defined above.

Table 6. Laboratory Data and Vital Sign Visit Windows (Post-Treatment Period)

Scheduled Time	Nominal Day (Study Drug End Day)	Time Window (Study Drug End Days Range)
Post-Treatment Week 4	28	3 to 56
Post-Treatment Week 12	84	57 to 126
Post-Treatment Week 24	168	127 to 266
Post-Treatment Week 52	364	267 to 546
Post-Treatment Week 104	728	547 to 910
Post-Treatment Week 156	1092	911 to 1274
Post-Treatment Week 208	1456	1275 to 1638
Post-Treatment Week 260	1820	1639 to 2002
Final Post-Treatment Visit ^a		> 2 days after last dose of study drug

a. The last value within the Post-Treatment Period window will be used to define the final post-treatment value. The lower bound of this Final window is Study Drug End Day 3.

Note: The result closest to the scheduled time point will be used. Data must also have Study Drug End Day > 2. Vital signs and hematology, chemistry, urinalysis, and coagulation panels are collected at every Post-Treatment Period visit. Total Insulin is collected at Post Treatment Weeks 52, 104, 156, 208, and 260 and will use those visit windows as defined above. FibroTest samples are collected at Post-Treatment Weeks 12 and 24 (or upon study discontinuation) and will use those visit windows as defined above.

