7.1 Demographic and Baseline Characteristics

Demographics include age, weight, height and BMI as continuous variables, and sex, race, ethnicity, age category (< 55 years or ≥ 55 years] and [< 65 or ≥ 65 years]), birth year (< 1945 , 1945 to 1965, > 1965), country, and BMI category (< 30 kg/m² or ≥ 30 kg/m²).

Baseline characteristics will include: HCV genotype 1 subtype (1a, 1b, 1-other), IL28B genotype ([CC, CT, or TT] and [CC or non-CC]), prior treatment history (treatment-naïve [IFN-eligible, IFN-ineligible] or IFN-based treatment-experienced [null responder, partial responder, relapser, relapse/breakthrough, nonresponder, IFN or pegIFN intolerant]), baseline HCV RNA levels ([continuous {use log₁₀ HCV RNA}] and [$< 800,000$ IU/mL or

$\geq 800,000$ IU/mL]), baseline HOMA-IR (< 3 or ≥ 3 mU \times mmol/L²), baseline fibrosis stage (F0-1, F2, F3, or F4), baseline Child-Pugh score (non-cirrhotic, 5, 6, or > 6), baseline FibroTest score, baseline albumin (continuous), baseline albumin (< 35 or ≥ 35 g/L), baseline creatinine clearance (GFR by Cockcroft Gault) (Continuous; < 30 mL/min, $\geq 30 - 49$ mL/min, $\geq 50 - 89$ mL/min, or ≥ 90 mL/min), baseline GFR by MDRD (continuous; < 30 , $30 - 59$, $60 - 89$, ≥ 90 mL/min/1.73m²; < 60 mL/min/1.73m² or ≥ 60 mL/min/1.73m²), baseline platelet count (continuous; $< 90 \times 10^9/L$ or $\geq 90 \times 10^9/L$; $< 50 \times 10^9/L$ or $\geq 50 \times 10^9/L$; $< 100 \times 10^9/L$ or $\geq 100 \times 10^9/L$; and $< 150 \times 10^9/L$ or $\geq 150 \times 10^9/L$), tobacco (user, ex-user, or non-user) and alcohol (drinker, ex-drinker, or non-drinker) use status, history of diabetes, history of depression or bipolar disorder, history of bleeding disorders, AST to platelet ratio index (APRI) (continuous; ≤ 2.0 or > 2.0), and Fibrosis-4 score (FIB-4) (continuous; ≤ 3.25 or > 3.25).

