10.5 Efficacy Subgroup Analysis

The analysis on SVR₁₂ status as described in Section 10.4 will be performed on the ITT-II population for the following subgroups (assessed at baseline), as appropriate:

- The presence of cirrhosis and subgenotype (GT1b without cirrhosis, GT1b with compensated cirrhosis, GT1 non-b without cirrhosis, and GT1 non-b with compensated cirrhosis);
- prior treatment history (treatment-naïve [IFN-eligible, IFN-ineligible] or IFN/RBV treatment-experienced [null responder, partial responder, relapser, relapse/breakthrough, nonresponder, IFN or pegIFN intolerant]);
- IL28B ([CC, CT, TT] and [CC or non-CC]);
- Sex (male or female);
- Age (< 55 or ≥ 55 years) and (< 65 or ≥ 65 years);
- Birth year (< 1945, 1945 to 1965, > 1965);
- Race (Black or Non-Black; Black will include any subject who marks 'Black or African American' for race on the Demographics eCRF);
- Ethnicity (Hispanic or Latino, Not Hispanic or Latino);
- BMI (< 30 or ≥ 30 kg/m²);

- Baseline HCV RNA levels ($< 800,000$ or $\geq 800,000$ IU/mL; below median or above or equal to median);
- Baseline GFR by Cockcroft Gault (< 50 or ≥ 50 mL/min);
- Baseline GFR by MDRD (< 30 , $30 - 59$, $60 - 89$, ≥ 90 mL/min/1.73 m²; < 60 or ≥ 60 mL/min/1.73 m²);
- Baseline HOMA-IR (< 3 or ≥ 3 mU \times mmol/L²);
- History of Depression or Bipolar Disorder (yes/no);
- History of Bleeding Disorders (yes/no);
- Baseline Child-Pugh score (< 5 , 5 , 6 , or > 6);
- Baseline fibrosis stage (F0-F1, F2, F3, or F4);
- APRI (≤ 2.0 or > 2.0);
- FIB-4 (≤ 3.25 or > 3.25);
- Any of APRI > 2.0 and FIB-4 > 3.25 , or neither.

For subjects with cirrhosis only:

- Baseline platelets ($< 50 \times 10^9/L$ or $\geq 50 \times 10^9/L$; $< 90 \times 10^9/L$ or $\geq 90 \times 10^9/L$; $< 100 \times 10^9/L$ or $\geq 100 \times 10^9/L$; $< 150 \times 10^9/L$ or $\geq 150 \times 10^9/L$);
- Baseline albumin (< 35 or ≥ 35 g/L);
- Platelets $< 90 \times 10^9/L$ or albumin ≥ 35 g/L, or neither of the two.

For GT1 non-b subjects with cirrhosis only:

- Treatment Duration (12 weeks or 24 weeks).

Each subgroup analysis will be performed if there are an adequate number of subjects within each subgroup. The two-sided 95% Wilson score confidence interval for a binomial proportion (percentage of subjects achieving SVR₁₂) will be produced if there are at least 10 subjects in the subgroup.

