11.3.2 Statistical Methods

Clinical laboratory tests will be summarized at each visit during the Treatment Period. The baseline value will be the last measurement on or before the day of the first dose of study drug. This same baseline value will be used for all change from baseline tables in the Treatment Period and Post-Treatment Periods.

Mean changes from baseline to each post-baseline visit, including applicable post treatment visits, will be summarized for each protocol-specified laboratory parameter with the baseline mean, visit mean, change from baseline mean, standard deviation, and median.

Laboratory data values will be categorized as low, normal, or high based on normal ranges of the laboratory used in this study. Shift tables from baseline to minimum value, maximum value, and final values during the Treatment Period (Study Drug End Day ≤ 2) will be created. The shift tables will cross tabulate the frequency of subjects with baseline values below/within/above the normal range versus minimum/maximum/final values below/within/above the normal range.

The number and percentage of subjects with post-baseline values during the Treatment Periods meeting the specified criteria for Potentially Clinically Significant (PCS) laboratory values (defined in [Table 8](#) and [Table 9](#)) will be summarized. A post-baseline

e value must be more extreme than the baseline value to be considered a PCS finding. A separate listing will be provided that presents all lab values for the subjects meeting PCS criteria during treatment.

For hemoglobin and the liver function tests (LFTs) of alkaline phosphatase and total bilirubin, the number and percentage of subjects with a maximum Common Terminology Criteria for Adverse Events (CTCAE) Grade of 1, 2, 3, or 4 (see definitions in [Table 10](#)) at any post-baseline visit (regardless of the baseline value) through the end of treatment (i.e., Final Treatment Value) will be summarized. All LFT tables will include summary rows for the number and percentage of subjects with at least Grade 2 and at least Grade 3 laboratory abnormalities. The hemoglobin table will include a summary row for the number and percentage of subjects with at least a Grade 2 laboratory abnormality.

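### SAP 11.3.2 ignores fasting status, so glucose and triglyceride summaries compare a baseline meant to be fasted with possibly fed values in a single-arm study

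*Protocol*

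**What the plan says.** **Sampling (Protocol 5.3.1.1, Clinical Laboratory Tests).** A fast of at least 8 hours is requested, as an ideal, at Day 1, the Final Treatment Visit and Post-Treatment (PT) Weeks 52, 104, 156, 208 and 260. For all others, "The remaining visits may be non-fasting". Day 1 calls for a fasting pre-dose sample, with a fallback for a subject who has not complied: "Blood samples should still be drawn if the subject did not fast for at least 8 hours". The information needed to tell the states apart is collected: "Fasting status will be recorded in the source documents and on the laboratory requisition".

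**Analysis (SAP).** The SAP text does not mention fasting.
- Section 11.3.2: mean change from baseline to each post-baseline visit "will be summarized for each protocol-specified laboratory parameter". Shift tables run to the minimum, maximum and final on-treatment value. On-treatment values are counted against the PCS limits of Table 9.
- Section 11.3: local laboratory values and extra tests done because of serious adverse events are included in all analyses.
- Section 6.1.1: baseline is the last non-missing pre-dose value, with no condition on fasting.
- Sections 7.1 and 10.5: "baseline HOMA-IR", cut at 3, is a baseline characteristic and an SVR12 subgroup. Section 10.5 also makes it a candidate in the stepwise logistic regression. Section 10.3 brings it into the Cox models, which take all Section 7.1 characteristics.

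**Grading (Protocol Appendix C).** High glucose and high triglycerides are both labelled as fasting; the glucose row label begins "GLUCOSE, SERUM, HIGH (Fasting".

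**The concern.** Glucose and triglycerides depend on recent food. A change from a fasted baseline to a fed visit contains a meal effect as well as any treatment effect, and the planned summaries cannot separate them. Two features make this worse. The study has one arm, so no concurrent group would show or cancel the artefact. Maximum-value shifts and any-value PCS counts also tend to pick out fed samples. A rise at Weeks 2 and 4 followed by a fall at the Final Treatment Visit could come from the sampling schedule alone and be read as a metabolic effect of the regimen.

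HOMA-IR raises a related but smaller question. If a Day 1 sample was not fasted, a subject can fall on the wrong side of 3 in the baseline table, the subgroup analysis and the regression models.

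**Working it through.** The plan states no figure on this point, so there is none to reproduce. The check sets the visit schedule against the list of fasting visits.

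**1. Visits.** Schedule from Protocol Table 7 and its notes; fasting visits from Protocol 5.3.1.1; insulin schedule from the SAP Table 5 and Table 6 notes.

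| Analyte, subjects | Post-baseline visits | Non-fasting allowed at | Count |
|---|---|---|---|
| Glucose, triglycerides; 12-week | Weeks 2, 4, EOT; PT 4, 12, 24, 52, 104, 156, 208, 260 | Weeks 2, 4; PT 4, 12, 24 | 5 of 11 |
| Glucose, triglycerides; 24-week | as above plus interim Week 12 | as above plus interim Week 12 | 6 of 12 |
| Insulin; 12-week | EOT; PT 52, 104, 156, 208, 260 | none | 0 of 6 |
| Insulin; 24-week | as above plus interim Week 12 | interim Week 12 | 1 of 7 |

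Shifts and PCS counts use on-treatment values only. There, non-fasting is allowed at 2 of 3 scheduled visits for 12-week subjects (Weeks 2 and 4, not EOT) and 3 of 4 for 24-week subjects (Weeks 2, 4 and 12, not EOT).

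**2. Week 12 window.** SAP Table 5 assigns Study Days 57 to 126 to Week 12, and SAP 5.1.3 presents all subjects together. For 12-week subjects this window holds the final treatment visit, where fasting is requested. For 24-week subjects it holds the interim visit, where it is not. One table row therefore mixes both states.

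**3. PCS limits.** SAP Table 9 flags glucose above 250 mg/dL and triglycerides above 500 mg/dL. These are the values at which Grade 3 starts in Appendix C, where both analytes carry the fasting label. The SAP uses the same numbers without that label.

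**4. HOMA-IR.** It is used only at baseline, and Day 1 is a fasting visit, so no sample is non-fasting by design. A fed value can still enter because the fast is only an ideal, because unfasted subjects are still sampled, and because the last-non-missing rule could supply a Screening glucose. The documents do not give the share *u* not fasted on Day 1. For illustration:

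share misclassified = *u* × P(3/*k* < fasting HOMA-IR < 3)

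Here *k* is the factor by which a fed state inflates HOMA-IR. Assumed values, none from the documents: lognormal HOMA-IR with median 2 to 4, log-SD 0.6 to 0.8, and *k* from 1.5 to 6.
- Smallest band (median 4, log-SD 0.8, *k* = 1.5): 0.166.
- Largest band (median 2, log-SD 0.6, *k* = 6): 0.740.
- *u* = 0: 0%. *u* = 2%: 0.3% to 1.5%. *u* = 10%: 1.7% to 7.4%. *u* = 20%: 3.3% to 14.8%.

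**5. Effect of setting unfasted HOMA-IR to missing.** At *u* = 2%, 10% and 20%, 600 × *u* = 12, 60 and 120 subjects in this study would have no value. SAP 6.3 does not impute baseline covariates, so a complete-case Cox model would drop them. On the SAP 4.3 assumptions, that model has 4% × 2,000 = 80 subjects without SVR12, and 20% × 80 = 16 composite events among them before dropout. If 10% of subjects were lost evenly across both studies, about 8 of those subjects and 1.6 of those events would go.

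**The case against.** The best defence is that little depends on these summaries. Glucose, triglycerides and insulin define no primary or secondary endpoint, Protocol 5.6.1 calls the analyses descriptive, and the HOMA-IR subgroup is one of about twenty. Appendix C serves toxicity management, while Table 9 is a separate screen that also requires a value more extreme than baseline. Non-fasting is permitted at the other visits, not required.

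Much of this stands, and it limits the point to a cheap improvement. It does not remove it. The more-extreme-than-baseline rule gives no protection when baseline is fasted and the later value is fed. Descriptive safety tables in a single-arm study are read without a comparator, so a systematic difference in sampling state matters there.

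Several stronger readings are tempting but not supported:
- *The HOMA-IR split misclassifies subjects by design.* Day 1 is a designated fasting visit, and the still-draw sentence is a fallback. Misclassification is possible but of unknown frequency.
- *Insulin summaries are broadly contaminated.* On the SAP schedule, the only insulin visit outside the fasting list is interim Week 12 in 24-week subjects, who come from at most 150 F4 subjects.
- *There is no baseline insulin sample.* The Total Insulin row of Protocol Table 7, as read from the PDF, appears to mark Week 2 and not Day 1. The SAP Table 5 note says "Total Insulin is measured at baseline, Week 12, Week 24". The column may have shifted in extraction, so this calls for a check and no more.
- *Table 9 contradicts Appendix C.* They serve different purposes; the shared cut-offs only show that the SAP's limits have no stated sampling condition.

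**Conclusion.** The point holds for glucose and triglycerides. Followed as written, SAP 11.3.2 compares a baseline meant to be fasted with values that may be fed at 5 of 11 post-baseline visits (12-week subjects) or 6 of 12 (24-week subjects), and it mixes both states in the Week 12 row. These counts come from the documents' schedules and need no assumption about compliance. The resulting bias in mean change or PCS counts cannot be computed, because the documents give neither the share of fed samples nor the fed-to-fasted difference.

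For insulin the exposure is one visit in one subset. For HOMA-IR it is a possible misclassification at the cut of 3: zero if everyone fasts on Day 1, and about 2% to 7% of subjects if 10% do not, on assumed distributions. A reader might infer that the primary or secondary endpoints are affected. Their definitions are not; HOMA-IR reaches the primary analysis only as one covariate among many.

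**What to change.** **SAP 11.3.2.** Base change from baseline and shifts for glucose and triglycerides on samples recorded as fasting, at baseline and post-baseline alike. Apply the same rule to insulin, where it matters mainly at interim Week 12. Show non-fasting values separately and labelled, with a further label for unknown status, which local laboratory values may need. Keep every PCS value but flag it by fasting status, so that no safety signal is lost.

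**SAP 7.1 and 10.5.** Derive baseline HOMA-IR from same-day, pre-dose insulin and glucose recorded as fasting, and state the formula.

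**SAP 10.3.** Put subjects without a fasting HOMA-IR in a missing category, or leave HOMA-IR out of the Cox models, so that they are not dropped. The models pool both studies, so check the fasting rules of TOPAZ-I, which these documents do not give.

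**Insulin schedule.** Check the Total Insulin row of Protocol Table 7 against the original and reconcile it with the SAP Table 5 note.

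**Cost.** SAP wording and programming. Fasting-only tables keep 6 scheduled post-baseline visits for glucose and triglycerides (of 11 or 12) and 6 for insulin (of 6 or 7). Some rows will hold fewer values; how many fewer is unknown. The protocol puts fasting status in source documents and on the requisition but does not say that it reaches the database, so that transfer must be arranged.
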